- Age over 18 years;
- Disease duration ≤ 48 months;
- Score ≥ 2 at the item "swallowing" of the ALS Functional Rating Scale-Revised (ALSFRS-R);
- Score ≥ 1 at the item "walking" of the ALSFRS-R;
- Score ≥ 1 at the item "respiratory insufficiency" of the ALSFRS-R
- Signature of informed consent.

EXCLUSION CRITERIA for patients:

- Motor neuron diseases other than ALS;
- Diagnosis of dementia according to current clinical criteria;
- Severe head trauma in the past;
- Persons carrying static electrical stimulators (e.g. cardiac stimulators, nerve stimulators, auditory implants) that would not work or would be damaged by the magnetic field;
- Persons carrying special metallic foreign bodies (e.g. splinters, some prostheses, screws and nails) that could move if placed inside the magnetic field;
- People with a history of epilepsy or seizures;

CLINICA NEUROLOGICA - UNIVERSITA' DEGLI STUDI DI BRESCIA
UO Neurologia 2 - AZIENDA SOCIO SANITARIA TERRITORIALE degli SPEDALI CIVILI DI BRESCIA

Direttore: [name]

- History of ischemic stroke or hemorrhage;
- Severe comorbidity
- Given that the effects of TMS on the developing fetus are not known, pregnant women will be excluded from the study.

STUDY DESIGN:

This is a non-pharmacological, randomized double-blind controlled clinical trial. This study does not present sub studies. Patients will be randomized into two groups: each group will receive anodal bilateral motor cortex tDCS and cathodal spinal tDCS (real tDCS) or sham stimulation for 5 days/week for 2 weeks, in a 2:1 ratio respectively.

END POINTS:

The long-term effect of tDCS on clinical parameters (ALSFRS-R, ALSAQ-40, CBI, EQ-5D-5L, muscle strength assessed with the MRC scale in different muscle districts), and neurophysiological measures (SICI and ICF).

For efficacy analyses, the primary end point will be the defined as change from baseline in global MRC scores. Secondary end points will be defined as changes from baseline in the ALSFRS-R, ALSAQ-40, EQ-5D-5L, EQ-VAS, CBI and intracortical connectivity (SICI and ICF).

STATISTICAL PLAN:

Parametric analysis (t test) will be used to compare the demographic variables (e.g. age, duration of illness, education) of the various groups at the baseline. A p -value <0.05 will be considered significant.

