In order to estimate the sample size, in order to obtain a significant difference in the primary outcome (Global MRC Score), we performed a "power analysis" based on the effects observed in a small group of patients (pilot study). The "effect size" $f(V)$ was calculated by direct method. Taking into account from previous observations a "partial $\eta^2 = 0.31$, equal to an "effect size" $f(V) = 0.67$ and, considering alpha = 0.05 and the power (1- β) = 0.80, considering a variable as covariate, the sample size expected for two patient groups (real and sham) is 25 total subjects using a repeated-measure ANCOVA study. The proposed sample size of 30 patients should be adequate to achieve the main objective of the study and would allow monitoring for confounding factors or drop-out patients.

Considering the unneglectable number of drop-out patients, that characterize most trials in ALS, we performed intention-to-treat and per-protocol analysis to reduce any bias due to the possible unbalanced drop-out rates between treatment groups. For

patients with missing values, data were assigned using mixed effects models for repeated measures without any ad hoc imputation.

To assess the effect of tDCS treatment on clinical scores over time, we will use a two-way repeated measure ANCOVA with TIME (T0, T1, T2 and T3) as within-subject factors and TREATMENT (sham vs real stimulation) as between-subjects factor, and the baseline values of each score as covariate, to reduce possible effects of baseline impairment on clinical score changes over time.

To assess the effect of tDCS treatment on TMS parameters we will use a two-way mixed ANOVA with TIME (T0, T1, T2 and T3) as within-subject factors and TREATMENT (sham vs real stimulation) as between-subjects factor.

When a significant main effect was reached, *post hoc* tests with Bonferroni correction for multiple comparisons will be conducted to analyze group-differences at respective time points. Mauchly's test will be used to assess for assumption of sphericity, while Greenhouse-Geisser epsilon determination will be used to correct in case of sphericity violation. Spearman's rank-order correlations will be used to assess associations between the improvement in clinical scores and neurophysiological parameters. Statistical analyses will be performed using SPSS version 21 (SPSS, Inc., Chicago, IL, USA).

ETHICAL CONSIDERATIONS (RISK-BENEFIT):

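### The only efficacy test named, a repeated-measures ANCOVA over T0–T3, does not by itself give the promised intention-to-treat analysis, and the mixed model probably intended is not named as the test

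*Combined protocol and SAP*

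**What the plan says.** All but one of these statements are in the protocol's STATISTICAL PLAN.

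- **Drop-out is expected.** The paragraph on it opens "Considering the unneglectable number of drop-out patients, that characterize most trials in ALS". No rate is given.
- **Analysis sets.** It continues: "we performed intention-to-treat and per-protocol analysis to reduce any bias due to the possible unbalanced drop-out rates between treatment groups". Neither set is defined, and neither is called primary.
- **Missing values.** For patients with gaps, "data were assigned using mixed effects models for repeated measures without any ad hoc imputation". This is the only mention of a mixed-effects model. No fixed effects, covariance structure, estimation method or treatment contrast are given.
- **Efficacy test for clinical scores.** "we will use a two-way repeated measure ANCOVA with TIME (T0, T1, T2 and T3) as within-subject factors", with TREATMENT as the between-subjects factor "and the baseline values of each score as covariate". On assumptions, "Mauchly's test will be used to assess for assumption of sphericity", with a Greenhouse-Geisser correction if needed.
- **Sample size.** "the sample size expected for two patient groups (real and sham) is 25 total subjects using a repeated-measure ANCOVA study"; 30 are planned.

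Under END POINTS, "the primary end point will be the defined as change from baseline in global MRC scores". No visit is named. The plan also does not say whether TREATMENT or TIME x TREATMENT carries the primary test.

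**The concern.** The promise and the named test do not match. A classical repeated-measures ANCOVA, the kind for which Mauchly's test is run, needs one complete row of T0–T3 values per patient. A patient who misses one visit is left out, so the result describes completers and not everyone randomised.

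The missing-data sentence does not close the gap, because it can be read in two ways:

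1. The mixed model is itself the analysis, fitted to the observed data. The ANCOVA and its sphericity steps are then not the ITT test, and the plan should say so.
2. The mixed model supplies values that are then put into the ANCOVA. If each gap receives one prediction that is treated as observed, the standard error is too small.

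Two analysts could follow the text faithfully and run different primary tests. With 30 patients at 2:1, sham has about 10, so a few losses matter. The reason given for the per-protocol analysis fails on any reading: excluding more patients after randomisation cannot be relied on to reduce bias from unbalanced drop-out.

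**Working it through.** **1. The plan's own sample size.** Inputs from the STATISTICAL PLAN: partial η² = 0.31, alpha 0.05, power 0.80, two groups. Then f = √(0.31/0.69) = 0.670, which matches the stated f(V) = 0.67. For the group-by-time test take λ = f² × N, df1 = m − 1, df2 = N − m, where m is the number of measurements and no degree of freedom is taken for the covariate. Power is the probability that a non-central F exceeds the 5% critical value.

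- m = 3, N = 25: λ = 0.4489 × 25 = 11.22, critical F(2, 22) = 3.44, power 0.805. This reproduces 25.
- m = 4 (T0–T3, as the analysis is written), N = 25: same λ, critical F(3, 21) = 3.07, power 0.728. Reaching 0.80 takes N = 29 (λ = 13.02, power 0.809).

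The plan does not state m, so m = 3 is inferred from the match.

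| Patients in the test | Power, m = 3 | Power, m = 4 |
|---|---|---|
| 30 | 0.88 | 0.83 |
| 25 | 0.81 | 0.73 |
| 24 | 0.79 | 0.70 |
| 22 | 0.74 | 0.65 |
| 20 | 0.69 | 0.59 |

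The decline is gradual; nothing special happens at 25.

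**2. Simulation of the alternatives.** All inputs here are assumptions: baseline MRC mean 75, SD 15; decline 2 points/month, SD 1.2; error SD 2.5 per visit; no floor or ceiling; arms of 20 and 10; loss at T3 only, of 17%, 25% or 33%. The visit times (0, 0.5, 2, 6 months) follow the protocol. The true-effect case slows real-arm decline by 1.5 points/month, giving 0.75, 3 and 9 points at T1, T2 and T3. The mixed model uses T1–T3 as outcome with baseline by visit, visit and arm by visit, unstructured covariance, REML and Kenward-Roger degrees of freedom.

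*Random loss, no true effect (5,000 runs each), rejection rate:*

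| Analysis | 17% | 25% | 33% |
|---|---|---|---|
| TIME x TREATMENT, complete cases | 5.3% | 4.9% | 5.1% |
| Mixed model, joint arm test over T1–T3 | 5.7% | 5.1% | 5.4% |
| TIME x TREATMENT, one filled-in value per gap | 9.2% | 10.9% | 13.7% |

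Across repeat runs, fill-in gave about 8–15% for TIME x TREATMENT and only about 6–8% for the TREATMENT main effect. Pooled multiple imputation (50 sets, 33% loss, T3 contrast) gave 3.9%, so the fault lies in single fill-in; the plan names no pooling step.

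*Random loss, true effect (4,500 runs each), power:*

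| Analysis | No loss | 17% | 25% | 33% |
|---|---|---|---|---|
| TIME x TREATMENT, complete cases | about 80% | 71% | 65% | 59% |
| Mixed model, joint arm test | about 60% | 55% | 51% | 48% |
| T3 contrast, complete cases | – | 68% | 64% | 57% |
| T3 contrast, mixed model | – | 73% | 70% | 65% |

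On the same data, the complete-case and mixed-model T3 verdicts differed in 9–15% of true-effect trials and 3–4% of null trials.

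*Loss that follows decline from T0 to T2 (real minus sham at T3, completers; MRC total is 100):*

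- Both arms, same rule, no true effect: bias within 0.1 points, rejection 5.1–5.5%.
- Both arms, same rule, true 9-point effect: bias about −0.5 to −0.8 at logit slope 0.3 and about −1.2 at slope 0.6, towards no effect.
- Sham only, no true effect: bias about −1.8 (slope 0.3) and −2.4 to −2.5 (slope 0.6). TIME x TREATMENT rejected in 6.6% and 9.4% (7.7% in a repeat of the steeper case). The mixed-model T3 bias was 0.01 and −0.04, with rejection 4.9% and 5.7%.

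**The case against.** The plan is not silent on missing data. It promises ITT, refers to mixed models and rules out ad hoc imputation. On the most natural reading a likelihood mixed model is intended, type I error is then kept, and the core defect is one of specification. That stands, and it limits the point.

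Three stronger readings are tempting, and the documents do not support them.

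- *That the plan excludes incomplete patients.* It nowhere says so. The exclusion is inferred from the procedure and its sphericity steps.
- *That the trial's false-positive rate would be about 9–14%.* That needs single predictions treated as observed, which fits poorly with the plan's rejection of ad hoc imputation. It also needs TIME x TREATMENT to be the primary term. The plan does not say that it is, and its post hoc rule refers to a main effect.
- *That the trial fails once fewer than 25 patients complete.* Power falls smoothly. The 25 itself is matched with three measurements, not with the four TIME levels in the analysis.

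It is also fair to say that the remedy brings only a modest gain, and that the joint mixed-model test had less power than the complete-case test under the assumed effect, which grows with time. Both are costs to weigh. Neither makes the written test an ITT analysis.

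**Conclusion.** The point holds as a mismatch that should be fixed: the test named for the primary end point does not by itself deliver the ITT analysis promised beside it, and the model that would do so is not named as the test. Confidence in that reading of the text is high.

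The harm is less certain. Every simulated figure rests on assumed variances, effect shape and T3-only loss. Under those inputs the main consequence is lost power. Complete-case type I error is sound if loss is random, or if it follows decline equally in both arms and there is no true effect. It would be wrong to infer that equal rules in both arms guarantee an unbiased estimate, because once a true effect exists the same rule pulls the estimate towards zero. The inflated error from fill-in belongs to the less likely reading. From the plan's own f(V), power for the four-level test is 0.73 at 25 patients. The per-protocol claim is unsupported whichever reading is taken.

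**What to change.** - Name as the primary ITT analysis of global MRC a likelihood-based mixed model for repeated measures in all randomised patients by assigned arm. Use observed T1–T3 values as outcome, baseline as covariate, arm, visit and arm x visit, a pre-stated covariance structure and small-sample degrees of freedom.
- Fill in no values. Remove the wording about assigning data and, for this model, the sphericity steps. Keep the repeated-measures ANCOVA as a completers' sensitivity analysis.
- Label per-protocol as supportive and delete the claim that it reduces drop-out bias.
- State in advance which arm term carries the primary test. This is the sponsor's choice. A joint test over T1–T3 keeps the TIME x TREATMENT hypothesis, since adjusting for baseline makes the T0 difference zero, but it had lower power here. A single-visit contrast changes the hypothesis; T3 would fit the stated long-term aim.
- Restate the sample size for the chosen term.

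The plan mixes past and future tense, so it is unclear whether data had been seen. If they had, state which analysis produced the primary result.

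**Cost.** No new data are needed, but this is more than rewording. The 25-patient calculation does not carry over. The model assumes that data are missing at random. Its gain over complete cases is modest: 5–8 power points for a T3 contrast in the simulation.

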Ten stimuli will be delivered for each ISI and fourteen control MEPs in response to the TS alone will be recorded, for each paradigm, in all participants in a pseudorandomized sequence. The amplitude of the conditioning MEPs will be expressed as a ratio of the mean unconditioned response. The inter trial interval will be set at 5 sec ($\pm 10\%$). All protocols will be performed in a randomized order in all participants. Throughout the experiment, complete muscle relaxation will be monitored by audio-visual feedback where appropriate.

All clinical and, neurophysiological evaluations will be performed at baseline (T0), after 10 tDCS applications i.e. at two weeks (T1), at two months (T2) and at six months (T3).

After the first evaluation (T0), the patients will be divided into two groups randomly. The first group will undergo a tDCS stimulation protocol, while the second group will undergo a placebo (sham) treatment. tDCS will be delivered by a battery-driven

CLINICA NEUROLOGICA - UNIVERSITA' DEGLI STUDI DI BRESCIA
UO Neurologia 2 - AZIENDA SOCIO SANITARIA TERRITORIALE degli SPEDALI CIVILI DI BRESCIA

Direttore: [name]

constant current stimulator (HDCstim, Newronika, Milan, Italy) through a pair of saline-soaked (0.9% NaCl) surface sponge electrodes. The anodes will be placed on the scalp over the motor cortex area and the cathode over the spinal cervical enlargement (over C6) (see Fig. 1B). The electrodes will be secured using elastic gauzes and an electroconductive gel will be applied to electrodes to reduce contact impedance (<5 kΩ for all sessions). During real stimulation a constant current of 2 mA per each anodal electrode (4.0×6.5 cm², current density 0.077 mA/cm²) and 4 mA per cathodal spinal electrode (5.0×7.5 cm², current density 0.107 mA/cm²) will be applied for 20 minutes. For the sham condition, the electrode placement will be the same, but the electric current will be ramped-down 5 seconds after the beginning of the stimulation to make this condition indistinguishable from the experimental stimulation. To detect differences in the perception of the stimulation, patients will be asked whether they thought they were receiving real or sham stimulation at the end of the two-weeks' treatment.

INCLUSION CRITERIA for patients:

- Male or female patients diagnosed with probable ALS, laboratory-supported, or defined according to current clinical criteria (World Federation of Neurology Revised El Escorial criteria - Brooks et al., 2000).

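### The clinical-score ANCOVA uses pre-randomisation T0 both as a TIME level and as the covariate, so its four-level TREATMENT effect is exactly 0.75 of the T1–T3 difference

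*Combined protocol and SAP*

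**What the plan says.** - **Procedures.** "All clinical and, neurophysiological evaluations will be performed at baseline (T0), after 10 tDCS applications", with later visits at two months (T2) and six months (T3). "After the first evaluation (T0), the patients will be divided into two groups randomly". T0 is therefore a pre-randomisation measurement.
- **End Points.** It states that "the primary end point will be the defined as change from baseline in global MRC scores". No visit is named.
- **Statistical Plan, clinical scores.** A "two-way repeated measure ANCOVA with TIME (T0, T1, T2 and T3) as within-subject factors and TREATMENT (sham vs real stimulation) as between-subjects factor", with "the baseline values of each score as covariate, to reduce possible effects of baseline impairment on clinical score changes over time".
- **Statistical Plan, missing values.** For "patients with missing values, data were assigned using mixed effects models for repeated measures without any ad hoc imputation". It gives no model terms and no covariance structure, and it does not say whether T0 stays an outcome row.
- **Statistical Plan, post hoc tests.** After a significant main effect, "tests with Bonferroni correction for multiple comparisons will be conducted to analyze group-differences at respective time points". Which main effect is meant, and how many comparisons are counted, is not stated.
- **Statistical Plan, sample size.** From a partial η² of 0.31, f(V) = 0.67, alpha 0.05 and power 0.80, "the sample size expected for two patient groups (real and sham) is 25 total subjects using a repeated-measure ANCOVA study"; 30 are planned. The model term to which 0.31 refers is not stated.

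The ANOVA for the TMS parameters has the same four TIME levels but no baseline covariate, so this point does not touch it.

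**The concern.** A baseline value can be used as an outcome level or as a covariate. Used as both in one model, it explains itself perfectly: at T0 there is no group difference left to estimate and no residual variation. Two consequences follow.

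First, any effect averaged over the four TIME levels includes one level that is zero by construction. The end point asks about change after baseline, and the plan names no primary contrast, so the four-level TREATMENT effect could be reported as the answer.

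Second, the plan expects appreciable drop-out and turns to mixed models. If T0 rows with zero residuals enter a model with one variance for all visits, they pull that variance down and make the T1–T3 comparisons look more precise than they are.

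**Working it through.** **1. The plan's own figure.** f² = 0.31/0.69 = 0.449, so f = 0.670, as stated. Take noncentrality f² × N (an assumed convention) and the multivariate group-by-time test for two groups and m levels, with df1 = m − 1 and df2 = N − 2 − (m − 1) + 1, one less with a covariate.
- m = 3, N = 25: df 2 and 22, power 0.806 (0.803 with the covariate). The stated 25 is reproduced.
- m = 4, N = 25: df 3 and 21, power 0.73 (0.72 with the covariate). N = 29 is needed for 0.80; N = 30 gives 0.83 (0.82).

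The stated 25 therefore fits three within-subject levels, not the four in the analysis text. The plan does not give the number of levels, so this is an inference.

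**2. Complete data.** For each patient, mean(T0…T3) = T0/4 + 0.75 × mean(T1…T3). In a regression on TREATMENT and T0, the T0/4 part is absorbed entirely by the T0 slope. The TREATMENT coefficient, the residuals, the SE and the interval are then all exactly 0.75 of those for mean(T1…T3). No SD or correlation is needed. In one simulated data set the four-level estimate was 2.216 (SE 1.267) and the T1–T3 estimate 2.954 (SE 1.689). The ratio is 0.750, and t = 1.749 in both, so the p-value is the same.

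**3. Mixed model with T0 rows, ANCOVA terms and one variance.** With equal residual variance σ² at T1–T3 (assumed), the pooled variance is (0 + σ² + σ² + σ²)/4 = 0.75σ², and the SE ratio at each visit is √0.75 = 0.866. Simulation (20:10 patients, residual SD 5, correlation 0.6, no drop-out; SD and correlation assumed) gave a mean SE of 1.70 with T0 and 1.96 without: 1.70/1.96 = 0.867. With 20% drop-out by T3 (assumed) the ratios were 0.85–0.88. With a single covariate slope for all visits they were 0.86–0.89.

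**4. Error rates under the null in that model.** With 30 − 3 = 27 df:
- At 0.05: 2.052 × 0.866 = 1.777, which is exceeded 7.6% (normal) to 8.7% (t) of the time. Simulated at correlation 0.6: 7.3–8.4%.
- At 0.05/3 = 0.0167: 2.552 × 0.866 = 2.210, which gives 2.7% to 3.6%. Simulated: about 3–3.5% without drop-out, 2.8–4.1% with 25% drop-out by T3 (assumed).
- Any false-positive visit at 0.0167 when TREATMENT must first be significant, correlations 0.3–0.8:

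| | with T0 | without T0 |
|---|---|---|
| no drop-out | 2.9–4.6% | 1.8–2.7% |
| 25% drop-out | 3.6–5.6% | 2.0–3.1% |

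- If either TREATMENT or TIME × TREATMENT may open the post hoc tests, the rate with T0 and 25% drop-out is 6.0–7.2%.

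**5. Unequal residual variance.** Assume SDs of 3, 5 and 7 at T1, T2 and T3, complete data.
- With T0: √((0 + 9 + 25 + 49)/4) = 4.56; SE ratios 4.56/3 = 1.52, 4.56/5 = 0.91, 4.56/7 = 0.65.
- Without T0: √(83/3) = 5.26; SE ratios 1.75, 1.05, 0.75.

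T1 is then too large and T3 too small in both. Removing T0 helps T3 but does not cure it.

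**6. Unstructured covariance with T0 rows.** With visit-specific covariate slopes the T0 residuals are zero. The REML log-likelihood then contains −(27/2) ln(T0 variance), which has no upper limit, so no finite maximum exists.

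**The case against.** The strongest reply is that the planned complete-data tests are sound. The TREATMENT p-value is the same with or without T0, TIME × TREATMENT is a valid test, and the visit-wise group differences at T1–T3, which the plan does announce, are untouched. The plan also never promises to report a four-level average. All of that stands, and it confines the complete-data harm to the size of the reported effect. It does not remove the point, because the specified TREATMENT effect is the four-level one and no other contrast is named as primary.

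It is also fair that the mixed-model consequence needs three things the plan does not state: the ANCOVA terms, T0 kept as an outcome row, and one common variance. That part is conditional.

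A reader might infer more than the documents support:
- *The primary test is invalid or loses power.* It is not and does not; estimate and SE shrink by the same factor.
- *The trial would run at about 8% false positives.* That is the rate for single-visit tests at 0.05, taken without any prior test. The plan requires a significant main effect first and a Bonferroni correction.
- *The T1–T3 standard errors are always too small.* This needs roughly equal residual variance at the three visits. In a progressive disease followed to six months, growing spread is plausible, and then the T1 standard error can be too large.
- *Bonferroni would be spent on an empty T0 comparison.* The plan states no family size.

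Finally, the remedy changes what one test does. Without T0, TIME × TREATMENT no longer detects a constant benefit. This is a real cost and is dealt with in the remedy.

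**Conclusion.** The point holds and should be fixed before analysis. The double use of T0 is explicit in the text, and the factor 0.75 is exact for complete data: a four-level TREATMENT effect reported as the change-from-baseline effect would be a quarter too small, with its interval scaled the same way.

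The drop-out consequence is a risk left open by an unspecified model. Under a common variance with T0 rows and equal T1–T3 residual variances, standard errors are about 0.87 of the truth. Under the plan's post hoc rule, read as a significant TREATMENT effect, the chance of any false-positive visit is about 3–6% with T0 against about 2–3% without. That is near nominal; it is higher if another effect may open the tests. The drop-out rates, SDs and correlations behind these rates are assumptions, since the documents give none. Confidence is high in the algebra and lower in how far the mixed-model part will apply.

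**What to change.** 1. Use T0 only as the covariate. Model T1, T2 and T3 with TREATMENT, TIME, TREATMENT × TIME, T0 score and T0 score × TIME, for the primary score and the clinical secondary scores.
2. Use the same outcome rows and terms in the mixed model for patients with missing values, and state its covariance: unstructured, or another structure with visit-specific variances. Unstructured has no finite maximum while T0 is both outcome and covariate; removing the T0 rows removes that obstacle.
3. Name the primary test: the TREATMENT effect averaged over T1–T3, or the difference at one named visit.
4. Limit post hoc group comparisons to T1–T3.
5. Tie the sample size of 25 to the named test and say which term the partial η² of 0.31 describes.

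The cost is SAP wording; patients, visits, data and software stay the same. The downside is that the primary test must be chosen. For a constant 5-point benefit (residual SD 5, correlation 0.6, 20:10 patients, assumed), TIME × TREATMENT has power 0.73 with T0 and 0.04 without, whereas TREATMENT over T1–T3 has 0.82. By the plan's f(V), under the noncentrality convention above, the planned 30 patients give at least 0.80 with three or four levels before drop-out.

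### The baseline covariate is not centred, so the TIME test in the primary MRC ANCOVA refers to a patient with an MRC score of 0; the treatment tests are unaffected

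*Combined protocol and SAP*

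**What the plan says.** The Statistical Plan fits a two-way repeated-measures ANCOVA to each clinical score. TIME (T0 to T3) is the within-subject factor, TREATMENT the between-subject factor, and the covariate is described as "the baseline values of each score as covariate". Its stated purpose is to limit the influence of baseline impairment on how scores change over time. Mauchly's test and the Greenhouse-Geisser correction are specified, and "Statistical analyses will be performed using SPSS version 21". Centring is neither stated nor excluded.

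Post hoc comparisons of the groups at each visit, with Bonferroni correction, are to follow "When a significant main effect was reached". The plan does not say which main effect is meant and does not mention the interaction. Missing values are to be handled by a mixed model for repeated measures whose covariate terms are not listed. The primary end point (End Points) is change from baseline in the global MRC score, which has a maximum of 100 (Procedures, clinical assessment).

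**The concern.** In a repeated-measures ANCOVA with a covariate crossed with TIME, the TIME main effect compares the visit intercepts, and an intercept is the expected score where the covariate equals zero. With raw MRC as covariate, that is a patient with no strength in any tested muscle group. Patients must score at least 1 on the ALSFRS-R walking item (Inclusion Criteria), so nobody near that value is likely to be enrolled. The test is therefore an extrapolation: imprecise, and aimed at a quantity of no interest.

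Two things are at stake. The trial could report no significant effect of time on its primary score in a disease the protocol calls progressive. And if TIME counts as a main effect for the post hoc trigger, a falsely non-significant TIME could help keep that step closed.

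**Working it through.** **1. The plan's own figure.** The sample size rests on "considering alpha = 0.05 and the power" of "0.80, considering a variable as covariate". Partial eta squared of 0.31 gives f(V) = sqrt(0.31/0.69) = 0.670. For the group-by-time interaction, take lambda = f(V)² x N, df1 = m - 1 and df2 = N - 2 - (m - 1) + 1, less 1 for the covariate. With m = 3 repeated measures and N = 25, lambda = 0.4493 x 25 = 11.23 on 2 and 21 df, and power is 0.803. This reproduces "is 25 total subjects using a repeated-measure ANCOVA study". (The four TIME levels named in the plan would need 29; that is a separate matter.) The calculation concerns the interaction, which step 5 shows does not depend on centring.

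**2. What TIME tests.** Let x be the baseline score and G the arm. The model at visit k is Y_k = a_k + b_k G + c_k x + error. Because T0 is both a TIME level and the covariate, the change to visit k is

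Y_k - x = a_k + b_k G + (c_k - 1) x + error.

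The TIME test asks whether the a_k are zero, that is, whether the change at x = 0 is zero. With x replaced by x minus its mean, it asks about the change at the average baseline.

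**3. Loss of precision.** The standard error at x = 0 relative to the mean is about sqrt(1 + (mean/SD)²). The means and SDs are assumptions:

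- mean 60, SD 20: sqrt(1 + 9) = 3.2
- mean 75, SD 15: sqrt(1 + 25) = 5.1
- mean 80, SD 10: sqrt(1 + 64) = 8.1

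**4. Power of the TIME test.** From the documents: N = 30 ("The proposed sample size of 30 patients should be adequate"), allocated "in a 2:1 ratio respectively", hence 20:10; four visits; alpha 0.05. Assumed: mean six-month loss 10, SD of change 8, measurement error SD 2. The slope is that of change on baseline, so the change tested at baseline 0 is -10 - slope x mean. Power is from simulation with the Greenhouse-Geisser correction.

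| Baseline mean, SD | Slope | Change tested at baseline 0 | Raw | Centred |
|---|---|---|---|---|
| 60, 15 | 0 | -10 | 0.30 | 1.00 |
| 75, 20 | 0 | -10 | 0.28 | 1.00 |
| 75, 15 | 0 | -10 | 0.20 | 1.00 |
| 75, 10 | 0 | -10 | 0.12 | 1.00 |
| 75, 15 | -0.133 (proportional loss) | 0 | 0.06 | 1.00 |
| 75, 15 | -0.4 | +20 | 0.64 | 1.00 |
| 75, 15 | +0.2 | -25 | 0.78 | 1.00 |
| 60, 20 | +0.2 | -22 | 0.96 | 1.00 |

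For loss unrelated to baseline, raw power runs from about 0.11 (mean 80, SD 10) to 0.45 (mean 60, SD 20). Proportional loss lowers it to about 0.05. At slope -0.4 a significant raw result reflects a gain of 20 points at baseline 0, although patients lose 10 on average. At +0.2 power is high, but the tested loss is 22-25 points rather than 10.

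**5. Treatment tests.** Shifting x by a constant alters the a_k but not the b_k. The simulated TIME x TREATMENT p-values agreed between raw and centred fits to within about 4e-14. TREATMENT is likewise a group coefficient and does not depend on the covariate's origin.

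**6. Post hoc step.** With an assumed treatment benefit, and either main effect allowed to open the step, it opened in 0.49-0.74 of trials raw and 0.94-1.00 centred. The chance of a significant visit comparison fell by only about 3-5 percentage points. The Bonferroni post hoc error with centring stayed near 0.04.

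**The case against.** The strongest reply is that the trial's question is untouched. The stated aim is the effect of tDCS over time, TIME pooled over arms is not an end point, and no efficacy p-value changes. That stands, and it sets the severity.

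The plan also does not say the covariate is uncentred or crossed with TIME. The first part stands as far as it goes: the raw score is the literal reading of a silent text. On the second, the covariate is meant to adjust changes over time, which a term not crossed with TIME cannot do, and the sphericity tests point to the standard repeated-measures procedure. The mixed model is different: if it omits baseline x TIME, centring does not affect its TIME test.

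Three stronger readings are tempting, and the documents do not support them.

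- A reader might infer that decline would usually be missed. No MRC mean, SD, rate of decline or slope is given, and the inference fails if weaker patients lose clearly more.
- A reader might infer that the report would misstate whether sham patients declined. TIME averages both arms, so it does not test sham decline, centred or not.
- A reader might infer that the real-versus-sham visit comparisons would be widely lost. TREATMENT can open the step too. In one set of assumed benefits it was significant in 80-100% of the trials with a significant interaction.

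Finally, a centred TIME test would open the post hoc step almost always, even with no treatment effect, so TIME would screen nothing. That is a fair argument for changing the trigger as well. It is no argument for leaving the reported TIME result uninterpretable.

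**Conclusion.** The point holds, as a free improvement of low severity. Followed literally, the plan tests TIME at a baseline MRC of 0. Under the assumed values, with loss unrelated or proportional to baseline, a real decline would be significant in about 5-45% of trials instead of about 100%. With other baseline-change relations raw power can be high, but the result still does not describe the patients enrolled. The figures depend on assumed MRC means, SDs, losses and slopes; the mechanism depends only on a raw covariate crossed with TIME. Only the MRC score was examined, so the size of the problem for the other clinical scales is not established. The randomised efficacy tests and the sample size are unaffected, and the cost to the post hoc step is small.

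**What to change.** In the Statistical Plan, describe the covariate as *the baseline value of each score, centred at the mean of all randomised patients*. Use the same centred variable in the mixed model wherever baseline is crossed with TIME. Separately, name TREATMENT or TIME x TREATMENT as the trigger for the post hoc visit comparisons, so that the step no longer depends on TIME. Changing the trigger alone would not correct the reported TIME result.

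The cost is a few words and one computed variable per score. Centring changes no treatment estimate, treatment p-value or sample size. Renaming the trigger changes only when the post hoc comparisons are run.
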